	
Countries where the pneumococcal vaccination administered will be PCV13 (Italy and Spain): 220 subjects will be randomized in a 1:1 ratio to one of the following 2 groups:
 
• Group 3: MenACYW conjugate vaccine (2+1 regimen) + PCV13 + Hexavalent vaccine + MMR vaccine (n=110)• Group 4: MenACYW conjugate vaccine (3+1 regimen) + PCV13 + Hexavalent vaccine + MMR vaccine (n=110) 
Subjects in Groups 1, 2, and 3 will receive either 3 doses of MenACYW conjugate vaccine or 3 doses of Nimenrix® administered concomitantly with routine vaccines at 2 months of age (Visit 1), 4 months of age (Visit 2), and 12 to 18 months of age (Visit 4). The hexavalent vaccines and the pneumococcal vaccines (PCV10 or PCV13) will be administered in a 2+1 regimen (ie, 2 doses in infancy and 1 final dose in the second year of life).
 
Subjects in Group 4 will receive 4 doses of MenACYW conjugate vaccine with routine pediatric vaccines at 2 months of age (Visit 1), 4 months of age (Visit 2), 6 months of age (Visit 3; MenACYW conjugate vaccine only), and 12 to 18 months of age (Visit 5; MenACYW conjugate vaccine and routine vaccines). The hexavalent vaccine and PCV13 will be administered in a 2+1 regimen, concomitantly with the 1st and 2nd doses in infancy and the 4th dose of MenACYW conjugate vaccine. The 3rd dose of MenACYW conjugate vaccine will be administered alone, without any other routine pediatric vaccines.
 
In all 4 vaccine groups, the MMR vaccine may be preferably administered concomitantly with the other vaccines at 12 to 18 months of age. If not, the subject will receive a licensed Measles, Mumps and Rubella vaccine with a gap of at least 4 weeks before any study vaccines or after the end of the study (ie, after the subject will have completed the last study procedure at the last study visit). When administered outside the study visit, the licensed Measles, Mumps and Rubella vaccine will be sourced by the health care system, according to the national immunization program.
 
Subjects in Finland, Sweden or Poland may receive the licensed rotavirus vaccine concomitantly with study vaccines at study vaccination visits Visit 1 and Visit 2. If not, the rotavirus vaccine can be administered with a time interval of at least 2 weeks before or 2 weeks after Visit 1 and/or Visit 2. The rotavirus vaccines will be sourced by the study sites and administered as per local standard practices. Safety data will be collected after its administration when done concomitantly with the study vaccine. No immunogenicity data will be evaluated after its administration.
 
Subjects in Spain, Czech Republic, and Poland will be offered 2 doses of the Meningococcal B vaccine (Bexsero®) when parents are willing to vaccinate their child within the second year of life. This vaccine is a non-study vaccine to be administered as per local standard practices at additional optional visits after the end of the trial (ie, after the subject will have completed the last study procedure at the last study visit). This vaccine will be outside the scope of the study evaluations. No immunogenicity and safety data will be collected after its administration. The Meningococcal B vaccine (Bexsero®) will be reimbursed by the Sponsor.

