With 716 enrolled subjects in Group 1 and in Group 2, the study will have a > 90% power (Farrington and Manning formula) to declare the non-inferiority of Group 1 versus Group 2 based on A, C, W, Y hSBA antibody titers $\geq 1:8$ (difference in the percentage of seroprotected subjects in the 2 groups) after 2 doses in infancy at 2 months and 4 months of age, assuming:

- An estimated 26.2% dropout rate from the PPAS (528 subjects evaluable per group)
- A 1-sided alpha level of 2.5%,
- A non-inferiority margin of 10% (percentage difference)

Table S2: Power of the study for the secondary objective

Antigen	Estimated Percentage of hSBA Titer $\geq 1:8$ Nimenrix®*	Non-inferiority margin†	Power
A	76%	10%	96.7%
C	94%	10%	> 99.9%
Y	71%	10%	94.7%
W	82%	10%	98.7%
Overall			90%

Since the hypothesis needs to be met for all serogroups, and the secondary objective is to be tested only if the primary objective succeeds, no alpha adjustment for multiple comparisons is necessary in these calculations.

* Percentages of subjects with an hSBA titer $\geq 1:8$ are based on the MET39 (NCT01049035) MenACYW 2/4/12 months schedule (Group 3) post dose 2 results using estimates 2% lower than in the MenACYW group. The power is calculated with the assumption that the estimates from the investigational group equal that of the control group corresponding to the estimated percentages in the Nimenrix® group described above.

† A non-inferiority margin of 10% has been widely used in previous studies evaluating the same antigens and in a competitor's study of the same type. Also taking into account the level of the reference rate taken in the Nimenrix® group, it is reasonable to use 10%.

The sample size has been arbitrarily set to 110 subjects in Group 3 and Group 4 as these data are not intended to be used for any hypothesis testing. No formal sample size calculations were performed. In each group, there is more than 95% probability to observe an event with an incidence of 2.7%.

In case of unexpected situation or any study hold resulting in an unexpected number of unevaluable subjects, total sample size may be increased to replace withdrawn, or unevaluable subjects.

Table of Study Procedures - Groups 1, 2, and 3

Phase III study, 5 visits, 3 vaccination visits, 4 telephone calls, 10 vaccine injections, 4 blood collections per subject,
11- to 17-month duration per subject

Visit/Contact	Visit 1	Telephone Call (TC) 1	Visit 2	TC2	Visit 3	TC3	Visit 4	TC4	Visit 5

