6.5 Randomization and Allocation Procedures

On the day of enrollment, subjects who meet the inclusion/exclusion criteria and whose parent / legally acceptable representative sign the ICF will be randomly assigned to Groups 1 through 4. Countries where PCV10 will be administered for pneumococcal vaccination, 1432 subjects will be randomized in a 1:1 ratio to 2 groups such that Groups 1 and 2 will have approximately 716 subjects each; and countries where PCV13 will be administered for pneumococcal vaccination, 220 subjects will be randomized in a 1:1 ratio to 2 groups such Groups 3 and 4 will have approximately 110 subjects each.

Randomization will be performed with permuted block method with stratification by center and age categories as follows: approximately 6 to 8 weeks (≥ 42 to ≤ 59 days), and 9 to 12 weeks (≥ 60 to ≤ 89 days).

^a All unexpected and related SAEs submitted to EU competent authorities must be unblinded.

The IRT system will also be used to allocate subjects in the rSBA subset in the countries included in the subsets as follows:

- 100 subjects randomized to Group 1; 100 subjects randomized to Group 2
- 50 subjects randomized to Group 3; 50 subjects randomized to Group 4

The rSBA subset will include subjects from all countries except Poland.

The vaccination / site staff will connect to the IRT system, enter the identification and security information, and confirm a minimal amount of data in response to IRT system prompts. The IRT system will then provide at least the vaccine dose number (except for the rotavirus vaccine) and subject number. The full detailed procedures for group allocation are described in the Operating Guidelines. If the subject is not eligible to participate in the study, then the information will only be recorded on the subject recruitment log.

Subject numbers that are assigned by the IRT system will consist of a 12-digit string (a 3-digit country identifier, a 4-digit study center identifier, and a 5-digit subject identifier). For example, Subject 724000100005 is the fifth subject enrolled in Center Number 1 in Spain (724 being the Spain country code).

Subject numbers should not be reassigned for any reason. The randomization codes will be kept securely in the IRT system.

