5.1.5.2 Safety

Safety results will be described for subjects in all study groups after any and each vaccination at 2, 4, 6 (only for Group 4) and 12 to 18 months of age (Visits 1, 2, and 4 for Groups 1, 2 and 3, and Visits 1, 2, 3 and 5 for Group 4). The main parameters for the safety endpoints will be described by 95% CI using the exact binomial method (Clopper-Pearson method).

At least the following parameters will be presented:

- Unsolicited systemic AEs reported in the 30 minutes after each vaccination, including occurrence, nature (Medical Dictionary for Regulatory Activities [MedDRA] preferred term), duration, intensity, action taken, relationship to the product administered, and whether the event caused termination from the study.
- Solicited (prelisted in the subject's diary card and CRB) injection site and systemic reactions starting any time from Day 0 (day of vaccination) through Day 7 after each vaccination,

including occurrence, time of onset, number of days of occurrence, intensity, action taken, and whether the reaction caused termination from the study.

- Unsolicited non-serious AEs reported up to 30 days after each vaccination, including occurrence, nature (MedDRA preferred term), time of onset, duration, intensity, action taken, relationship to the product administered, and whether the event caused termination from the study.
- SAEs (including AESIs) reported throughout the study, ie, from Visit 1 (first vaccination) to the last study visit (Visit 5 for Groups 1, 2, and 3 and Visit 6 for Group 4, occurring 30 days [+21 days] after the last vaccination), including occurrence, nature (MedDRA preferred term), time of onset, duration, intensity, action taken, relationship to the product administered, whether the event caused termination from the study, outcome, elapsed time from last administration (if less than 24 hours), relationship to study procedures, and seriousness criterion.

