5.2.3 Safety Analysis Set

The safety analysis set (SafAS) is defined as those subjects who have received at least one dose of the study vaccine(s) and have any safety data available. Specific safety analysis set will be defined and used after each vaccination. All subjects will have their safety analyzed after each dose according to the vaccine they received, and after any dose according to the vaccine received at the first dose. As participants in Group 3 and 4 have the same vaccines administered at 2, 4 and at 12 to 18 months of age, those two groups cannot be differentiated according to the vaccine received at the corresponding visit. Hence, for those two groups the following rules will be applied to determine the analysis actual treatment group for the first dose at 2 month of age and the second dose at 4 months of age:

- If the subject has received a dose of MenACYW at Visit 3 then the actual vaccination group is “Group 4”
- Else if the subject has received a dose of Group 3 study vaccines at Visit 4 then the actual vaccination group is “Group 3”
- Else, if the subject only received vaccination at 2 and/or 4 months of age, then the randomization group will be used to determine the actual vaccination group.

To determine the analysis actual treatment group for the vaccination at 12 to 18 months of age, the following rule will be used:

- If the subject has received a dose of study vaccines at Visit 5 then the actual vaccination group is “Group 4”, otherwise if the study vaccines are given at Visit 4 then the actual vaccination group is “Group 3”.

For each safety analysis set, safety data recorded for a vaccine received out of the protocol design will be excluded from the analysis (and listed separately).

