5.2.3.2 Safety Analysis Set for Vaccination at 2 Months of Age

The SafAS 1 for vaccination at around 2 months of age is defined as those subjects who have received the study vaccine at Visit 1 and have any safety data available. Subjects in Group 1 and 2 will have their safety analyzed after the Visit 1 dose according to the vaccines they actually received at Visit 1. Actual vaccination groups for Group 3 and Group 4 will be determined using the rule presented in [section 5.2.3](#).

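### Groups 3 and 4 have identical vaccines at 2 and 4 months, but the SAP specifies safety only per group of about 110, assigned by later visits under a rule that leaves one case undefined

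*Protocol*

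**What the plan says.** **Allocation.** In Italy and Spain, "220 subjects will be randomized in a 1:1 ratio to one of the following 2 groups" (protocol Synopsis and 5.1.3). Protocol 6.5 adds: "Randomization will be performed with permuted block method with stratification by center and age categories". MenACYW is open-label in both arms (protocol 6.4).

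**Exposure.** Protocol Tables 5.1 and 5.2 give both arms MenACYW, hexavalent vaccine and PCV13 at Visits 1 and 2. They first diverge at Group 4's Visit 3 dose, 60 (+14) days after Visit 2.

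**Sample size.** Protocol 12.5, repeated in SAP 5.5: "The sample size has been arbitrarily set to 110 subjects in Group 3 and Group 4". It continues: "In each group, there is more than 95% probability to observe an event with an incidence of 2.7" percent.

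**Grouping for safety.** Protocol 12.2.4 and 12.2.5 analyse safety after Visits 1 and 2 by the vaccines received at that visit. SAP 5.2.3 begins its exception with "As participants in Group 3 and 4 have the same vaccines administered at 2, 4 and at 12 to 18 months of age" and concludes that the visit's vaccines cannot separate the two groups. For doses 1 and 2 it then applies three branches in order:

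1. "If the subject has received a dose of MenACYW at Visit 3 then the actual vaccination group is" Group 4.
2. Otherwise, a child given Group 3 study vaccines at Visit 4 is Group 3.
3. Otherwise, a child vaccinated only at 2 and/or 4 months takes the randomised group.

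SAP 5.2.3.2 (SafAS1) refers back to this: "Actual vaccination groups for Group 3 and Group 4 will be determined using the rule presented in" section 5.2.3. SAP 5.2.3.3 (SafAS2) does the same, and SAP 5.7 records the derivation as a change from the protocol.

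**Display.** SAP 5.1.5.2: "Safety results will be described for subjects in all study groups after any and each vaccination at 2, 4, 6 (only for Group 4"), and at 12 to 18 months. No pooled Group 3+4 display is named in either document.

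**The concern.** At doses 1 and 2 the split between Groups 3 and 4 carries no treatment information: the vaccines, countries and randomisation are the same, and the schedules have not yet diverged. Under the protocol's own rule, safety by vaccine received at that visit, the two arms form one exposure group.

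Three things follow.

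- Each reported rate rests on about half the infants who had that exposure. Groups 3 and 4 are the only infants in the trial given MenACYW with PCV13 (Group 1's 716 receive PCV10), and protocol 5.1.2 gives data on that combination as a purpose of these groups.
- Events after the 2-month dose are placed in a column according to what the child received months later.
- The assignment rule is incomplete, so some children could have no defined column.

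**Working it through.** **Inputs.** Planned size is 110 per group, so 110 + 110 = 220 pooled (protocol 5.1.3, 12.5). The interval method is exact Clopper-Pearson, 95% (protocol 12.1.3, SAP 5.1.5.2). These are planned enrolment numbers and assume that all are vaccinated and contribute safety data.

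**Step 1: reproduce the plan's figure.** P(at least one event) = 1 − (1 − p)^n. With n = 110 and p = 0.027: 1 − 0.973^110 = 95.07%. The plan's statement of more than 95% is correct for one group.

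**Step 2: same quantities at n = 220.** The incidence seen at least once with 95% probability is 1 − 0.05^(1/n).

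| Quantity | n = 110 | n = 220 |
|---|---|---|
| Incidence detectable with 95% probability | 2.69% | 1.35% |
| P(at least one event) at 2.7% | 95.1% | 99.8% |
| P(at least one event) at 1% | 66.9% | 89.0% |

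**Step 3: exact 95% intervals.**

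| Observed rate | n = 110 | n = 220 | Width, 110 against 220 (points) | Ratio of widths |
|---|---|---|---|---|
| 0% | 0–3.30% | 0–1.66% | 3.30 against 1.66 | 1.99 |
| 10% (11/110, 22/220) | 5.10–17.19% | 6.37–14.75% | 12.09 against 8.37 | 1.44 |
| 30% (33/110, 66/220) | 21.63–39.48% | 24.02–36.52% | 17.84 against 12.50 | 1.43 |
| 50% (55/110, 110/220) | 40.32–59.68% | 43.20–56.80% | 19.37 against 13.59 | 1.43 |

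For observed rates of 10% to 50% the pooled interval is about 30% narrower (8.37/12.09 = 0.69; 13.59/19.37 = 0.70).

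**Step 4: are events lost by splitting?** At an incidence of 1.36%, one group of 110 shows at least one event with probability 77.83%. At least one event in either column: 1 − (1 − 0.7783)² = 95.08%. Pooled at n = 220: 95.08%. The two are equal, so splitting hides no event. It only widens each estimate's interval.

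**Step 5: trace the assignment rule.** Take a child randomised to Group 4, vaccinated at Visits 1 and 2, who misses Visit 3 and is vaccinated at Visit 5.

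- Branch 1 fails: no MenACYW at Visit 3.
- Branch 2 fails: no Group 3 vaccines at Visit 4, which in Group 4 is a blood-sampling visit.
- Branch 3 fails: the child was not vaccinated only at 2 and/or 4 months.

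No group results for doses 1 and 2. The separate rule for the 12-to-18-month dose does place this child in Group 4.

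**Step 6: which windows can be pooled?** After Visit 1, both groups return at 60 to 74 days. After Visit 2, the next visit is at 30 to 51 days in Group 3 and 60 to 74 days in Group 4. The immediate, D0–D7 and D0–D30 windows close before the exposures diverge at day 60 or later. The period from D31 to next visit, used for SAEs and AESIs in SAP 4.4.1.2.6 and 4.4.1.2.7, has unequal length after dose 2 and should not be pooled.

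**The case against.** The strongest reply is that this is table layout in a descriptive objective. Groups 3 and 4 represent two regimens (2+1 and 3+1), were never sized for precision and enter no hypothesis test, so showing each regimen dose by dose is a legitimate choice. SAP 5.1.5.2 also presents its list as a minimum, so a pooled table is not ruled out; its absence is inferred from silence. All of this stands, and it is why the group columns should stay and the pooled column be added beside them.

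Several stronger readings are tempting and are not supported:

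- A reader might infer that half the safety information is discarded, or that the trial can detect only events twice as common. Step 4 shows otherwise: all of about 220 infants are analysed, and an event in either column is visible.
- A reader might infer that the sample-size sentence is wrong. It is a correct per-group statement.
- A reader might infer that any Group 3 against Group 4 difference at these doses must be chance or misassignment. For dose 2, the diary is collected at 30 to 51 days in Group 3 and 60 to 74 days in Group 4, in open-label arms, so collection or recall could also differ.
- A reader might replace 110 and 220 with 88 and 176. The 88 is the per-protocol evaluable number; the safety sets require only the dose at that visit and some safety data.

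It is also fair to say that, for children who follow their schedule, the SAP rule returns the randomised group. The documents give no basis for estimating how many others there will be.

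**Conclusion.** The point holds as a precision and definition issue. For MenACYW with hexavalent vaccine and PCV13 at 2 and 4 months, the specified displays give intervals about 1.4 times as wide as the randomisation allows, and about twice the upper limit when no event is seen. Separately, the rule for doses 1 and 2 depends on later vaccinations and leaves one identifiable case without a group.

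The size rests on planned numbers of 110 and 220; smaller safety sets would widen both intervals. Pooling is justified by the shared randomisation and identical exposure, and only up to D30 after each of the two doses. It is not justified at 6 months, at 12 to 18 months or for any-dose summaries, where Group 4 has been scheduled for an additional MenACYW dose. No trial conclusion, and nothing in the Group 1 against Group 2 comparison, depends on this. It is worth doing because it is nearly free.

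**What to change.** - **SAP 5.1.5.2, 5.2.3.2 and 5.2.3.3:** add a pooled Group 3+4 column (about 220) beside the two group columns for SafAS1 and SafAS2. Limit it to the immediate, D0–D7 and D0–D30 windows. Exclude the period from D31 to next visit, the any-dose tables and everything from the 6-month dose onward.
- **SAP 5.2.3:** for any split by group at doses 1 and 2, use the randomised group in place of receipt at Visit 3 or Visit 4. This also closes the undefined case. SAP 5.2.3.1 points to the same rule for the any-dose set, so the undefined case needs an explicit assignment there too.
- **Protocol 12.5 and SAP 5.5 (optional):** state the pooled detectable incidence for these two doses, about 1.4%, next to the per-group 2.7%, which stays as it is.

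The cost is SAP wording, one extra column in the Visit 1 and Visit 2 safety tables, and a footnote that the dose 2 diary is collected at 30–51 days in Group 3 and 60–74 days in Group 4. No additional data or infants are needed.

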1.1 Background

This is a study using MenACYW conjugate vaccine (MenQuadfi[®]) against invasive meningococcal disease (IMD).

This study (MET58) will compare the immunogenicity and describe the safety of MenACYW conjugate vaccine and Nimenrix[®] when administered as a 3-dose series concomitantly with routine pediatric vaccines to infants and toddlers in Europe.

IMD is a serious illness caused by the bacterium *Neisseria meningitidis* (*N. meningitidis*), a Gram-negative diplococcus found exclusively in humans. Symptoms may include intense headache, fever, nausea, vomiting, photophobia, stiff neck, lethargy, myalgia, and a characteristic petechial rash (1). At least 12 different meningococcal serogroups have been classified based on the immunochemistry of the capsular polysaccharides (PS). Some strains are more likely than others to cause infection (1) (2) (3). Worldwide, most cases of meningococcal disease are caused by serogroups A, B, C, X, Y, and W (2) (3) (4). Serogroup B is responsible for endemic disease and some outbreaks, while serogroup C is responsible for large outbreaks (5). Serogroup A remains the main cause of epidemics in the world and is especially dominant in Africa and Asia. Serogroup W has been observed in Africa, as well as the United Kingdom, in residents who participated in the Hajj pilgrimage to the Kingdom of Saudi Arabia (4) (6) (7) and more recently in Chile (8), Turkey (9) (10), China (11) (12), Argentina (13), Brazil (14) (15), and other parts of the world. Serogroup X causes substantial meningococcal disease in parts of Africa, but rarely causes disease in other parts of the world (2) (16). Serogroup Y has not been associated with outbreaks, but the frequency with which it causes sporadic cases has gradually increased in the US and more recently in Canada and Europe (17) (18) (19). The Y serogroup is commonly associated with meningococcal pneumonia, particularly in older adults \geq 65 years of age (20). Outbreaks of serogroup B meningococcal disease have also been reported on college campuses in the United States (US) during the last five-year period: a prolonged outbreak of serogroup B on a university campus in Ohio from 2008 – 2010 and 2 universities in New Jersey and California in 2013 (21) (22).

The epidemiology of *N. meningitidis* can be described as complex, unpredictable, geographically variable, and changing over time. Meningococcal disease occurs worldwide in both endemic and epidemic forms with seasonal variation. In Europe, the incidence rate of IMD has remained stable over the last 5 to 10 years, with the highest peak occurring in the population less than 4 years of age and a smaller peak in the 15 to 19 year old group. The highest incidence rate in Europe is caused by serogroup B, followed by C (23) (24). The highest proportion of meningococcal cases was due to serogroup B in the population under 5 years of age. The highest proportion of serogroup C cases was observed in the population 25 to 44 years of age while the proportion of serogroup Y cases was highest in the population aged 65 years and above.

Surveillance data from England and Wales showed an increase in endemic meningococcal serogroup W disease across all age groups, accounting for 15% of all IMD cases in 2013 - 2014 compared with an average of 1% to 2% of all IMD cases in earlier years (25). A gradual increase in serogroup Y IMD has also been recently reported in England and Wales between 2007-2009

(26) and in Sweden during 2005 – 2012 (27) (28). Nearly 50% of all IMD in Sweden was caused by serogroup Y in 2012 (27). Similarly, an increase in the proportion of IMD caused by serogroup Y has been observed in other Nordic countries, accounting for 31% in Norway in 2009 – 2010 (29) and 38% in Finland in 2010 (30).

The goal for MenACYW conjugate vaccine is to provide broad protection against IMD caused by serogroups A, C, W, and Y in all age groups including children as young as 6 weeks of age, adolescents, and adults, including those 56 years of age and older.

